8.7.5. Unanticipated Adverse Events

Investigators shall submit to Endologix and to the reviewing EC/IRB a report of any unanticipated adverse device effect occurring during an investigation as soon as possible, but in no event later than 10 working days after the investigator first learns of the effect. Investigators must submit to Endologix documentation of the report made to the EC/IRB.

8.7.6. Protocol Deviations

Reports of any deviation from the protocol conducted in an emergency situation, to protect the life or physical well-being of a patient, will be reported to Endologix and to the EC/IRB as soon as possible, but no later than 24 hours from the time of the event.

8.7.7. Clinical Events Committee Review

Overview

The clinical events committee (CEC) identified in §2 consists of at least three physicians who will serve as independent experts responsible for evaluation and categorization of adverse events reported by the investigators in the trial. Analyses of events described in this protocol will be based on the CEC-determined categorization.

The primary purpose of these individuals is to ensure a consistent, independent review of events and their clinical significance using standardized criteria and definitions. A curriculum vita for each CEC member is maintained by Endologix, and is available for regulatory review. Due to the need for independence, these individuals may not participate in this trial as investigators, and may not hold significant material, financial or other interests which create a potential conflict with respect to this role, including but not limited to significant equity interest in Endologix.

Process

Endologix will provide independently to the CEC the complete case report form event text that details all deaths and the events as reported by the clinical site investigators. This information will be provided without identification of the site name, and will identify patients by identification number and initials only. Non-serious events or events that are reported as clearly unrelated events will not be assessed by the CEC. The CEC will review events and any follow-up data requested from Endologix. This may include copies of such documents as progress notes, operative notes, discharge summaries, death summaries, and autopsy reports.

The CEC will document the event categorization for each event individually. Meeting notes and supporting information, requests for documentation, etc. will be maintained.

Event Definitions

The following event definitions will be applied to the Primary Endpoint Analysis during this study. Where possible, events will be categorized as being related to the AAA procedure or related to the access site closure.

- *Death*: Any death occurring during the study period, regardless of cause.

Death will be further subcategorized as early (within 30 calendar days from the date of the procedure) or late (>30 days). It will also be subcategorized as aneurysm-related or not aneurysm-related.

Aneurysm-related death is defined as: any death occurring within 30 days from the date of the procedure, regardless of cause, and death due to aneurysm rupture or following any procedure intended to treat the aneurysm.

- *Procedural Technical Failure*: An event occurring procedurally or within 30 days post-procedurally that meets one or more of the following criteria:
 - *Aortic Stent Graft Failure* is defined as a failure of the bifurcated or fenestrated proximal extension stent graft to be delivered and deployed, such that the procedure is not completed, or the device failure results in a serious complication. The presence of a residual Type I or III endoleak that cannot be resolved during the index procedure is also included in this category.
 - *Renal Stent Graft Failure* is defined as a failure of the renal stent graft to be delivered and deployed, such that the procedure is not completed, or the device failure results in a serious complication.

- *Major Adverse Event*: An event occurring during the trial that meets one of the following criteria:
 - *All-Cause Death* (see above).
 - *Bowel Ischemia*: the lack of adequate blood flow to the intestines that requires intensification of medical therapy or surgical/endovascular intervention.
 - *Myocardial Infarction*: the presence of raised cardiac biomarkers in comparison to laboratory reference ranges.
 - *Paraplegia*: Paralysis of the lower extremities inclusive of the lower trunk.
 - *Renal Dysfunction*: a reduction in estimated glomerular filtration rate (eGFR) of >30% from baseline.
 - *Renal Failure*: the need for temporary or permanent dialysis or >0.5mg/dL increase in pre-operative serum creatinine level at two consecutive intervals.
 - *Respiratory Failure*: pneumonia or respiratory failure requiring ventilator support beyond 24 hours post-procedure.
 - *Stroke*: a sudden development of neurological deficit due to vascular lesions of the brain such as hemorrhage, embolism, or thrombosis that persists for >24 hours.
 - *Blood Loss $\geq 1,000$ cc*: Estimated blood loss during the index procedure $\geq 1,000$ cc.

- *Other Definitions*:
 - *Aneurysm Enlargement*: Core Lab reported aneurysm sac diameter increase of >5mm in late follow-up as compared to the initial post-operative measurement.
 - *Aneurysm Rupture*: internal bleeding or leaking of blood from the aneurysm subsequent to the index procedure.

- *Conversion to Open Repair*: open surgical repair of the abdominal aortic aneurysm due to unsuccessful delivery or deployment of the stent graft, due to complications or other clinical situations that precluded successful endovascular treatment, or at any time following initial successful endovascular treatment for any reason.
- *Cardiac Morbidity*: acute myocardial infarction (diagnosed based on measured levels of one or more cardiac biomarkers in comparison to laboratory reference ranges); new onset heart failure (an acute episode or exacerbation of existing low cardiac output accompanied by distal and/or pulmonary edema); intractable or malignant arrhythmia requiring cardioversion or pacemaker placement; or coronary intervention (coronary artery bypass grafting [CABG] or percutaneous coronary intervention [PCI]).
- *Clinically Significant Device Migration*: Core Lab reported aortic stent graft movement >10mm from the original implant location resulting in an intervention or in a serious complication.
- *Renal Dysfunction*: a reduction in the estimated glomerular filtration rate (eGFR) of >30% from the preoperative value.
- *Secondary Procedure*: any non-diagnostic intervention after the index procedure intended to correct or repair an endoleak, limb occlusion, migration, aneurysm sac expansion and/or a device defect.
- *Stent Graft Occlusion*: intervention for aortic or renal stent graft occlusion or as reported by the Core Laboratory at any time in follow-up.
- *Transient Ischemic Attack*: a sudden development of neurological deficit due to vascular lesions of the brain such as hemorrhage, embolism, or thrombosis that persists for <24 hours.
- *Type I/III/IV Endoleak*: Core Lab reported endoleak: between the endograft and the vessel either at the proximal attachment point (Type IA), or at the distal attachment point (Type IB), or between endograft components (Type III) or transgraft (Type IV).
- *Type II Endoleak*: Core Lab reported endoleak emanating from a patent collateral vessel (e.g., inferior mesenteric artery, lumbar artery).

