6. RESPONSE MEASURES

6.1. SAFETY

The safety endpoint is defined as the incidence of Major Adverse Events (MAE), defined as the composite of the following as determined by the independent Clinical Events Committee (CEC). Event definitions are provided in §8.7.7.

- *All-Cause Death;*
- *Bowel Ischemia;*
- *Myocardial Infarction;*
- *Paraplegia;*
- *Renal Failure;*
- *Respiratory Failure;*
- *Stroke;*
- *Procedural Blood Loss $\geq 1000cc$.*

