8.7. ADVERSE EVENT REPORTING

Throughout the course of the study, all adverse events will be recorded on the applicable **ADVERSE EVENT** CRF and in the patient's medical records. The seriousness, date of onset, date of resolution, severity, action taken, relationship to the device, and relationship to the procedure will be identified by the Investigator.

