8.7.1. General Definitions

An adverse event (AE) is any undesirable clinical occurrence in a patient administered a product and that does not necessarily have a causal relationship with the treatment. An AE can therefore be any unintended sign, symptom or disease temporally associated with the use of an investigational product, whether or not related to the use of the product.

A serious adverse event (SAE) is an AE that results in death, is life threatening, requires in-patient hospitalization or that prolongs hospitalization, results in persistent or significant disability/incapacity, or that is a congenital anomaly or birth defect.

An unanticipated adverse event (UAE) is any serious adverse effect on health or safety or any life threatening problem or death caused by or associated with a device, if that effect, problem, or death was not previously identified in nature, severity, or degree of incidence. Additionally, an unanticipated adverse event includes any other unanticipated serious problem associated with a device that relates to the rights, safety, or welfare of subjects.

Severity of an AE is a clinical determination of the event intensity. The severity assessment for a clinical AE should be completed using the following definitions as guidelines:

Mild (+1): Awareness of sign or symptom, but easily tolerated.

Moderate (+2): Discomfort enough to cause interference with usual activity.

Severe (+3): Incapacitating with inability to work or do usual activity.

NOTE: An event that is fatal should be recorded as death on the **ADVERSE EVENT** CRF. The cause of death will be detailed on the **Serious Adverse Events** section of the form.

Relationship to device or procedure of an AE is a judgment determination made by the Investigator that there is a logical connection between device use (e.g., delivery system manipulation) and the occurrence of the AE.

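### The primary MAE endpoint is to be determined by the CEC, but site labels of non-serious or clearly unrelated keep qualifying events from the CEC

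*Combined protocol and SAP*

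**What the plan says.** Four parts of the protocol bear on this.

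- **Who determines the endpoint.** §6.1 describes MAE as "defined as the composite of the following as determined by the independent Clinical Events Committee (CEC"). The synopsis sets the primary time point at 1 month.
- **What the analysis uses.** §8.7.7, Overview: "Analyses of events described in this protocol will be based on the CEC-determined categorization". On the component definitions, the same section adds: "The following event definitions will be applied to the Primary Endpoint Analysis during this study".
- **What the CEC sees and assesses.** §8.7.7, Process, supplies the committee with "the complete case report form event text that details all deaths and the events as reported by the clinical site investigators", and then restricts its work: "Non-serious events or events that are reported as clearly unrelated events will not be assessed by the CEC". §10.1 g) describes the committee's review with no such restriction.
- **Who assigns the labels.** §8.7 says: "seriousness, date of onset, date of resolution, severity, action taken, relationship to the device, and relationship to the procedure will be identified by the Investigator".

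No text in the material reviewed says how an unassessed event that meets an MAE definition is counted. The SAP is listed as Attachment 5 and the case report forms as Attachment 3, but the text of neither was available.

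**The concern.** The protocol gives the endpoint to an independent committee and then lets the sites decide which events that committee may classify. §8.7.7 says the CEC exists to give a consistent, independent review; a filter that runs on site labels works against that purpose.

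The study has a single arm, safety is a primary endpoint, and the results are meant to support US and CE Mark submissions. There is no control arm in which the same filter would operate and partly cancel out. Anything it removes comes straight off the reported MAE rate.

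Two further uses are affected. MAEs are also reported at 6 months and yearly to 5 years (§6.3), when a site is more likely to call a stroke or infarction unrelated. The DSMB reviews adjudicated events (§10.1 g and h), so filtered events may be missing from its data as well.

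**Working it through.** The plan states no MAE rate, performance goal or sample-size calculation for this endpoint, so there is no figure of its own to reproduce. The check has three steps.

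**1. Can a qualifying MAE carry a label that blocks assessment?**

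The serious-event definition in §8.7.1 depends on outcome: death, threat to life, disability, congenital anomaly, or an event that "requires in-patient hospitalization or that prolongs hospitalization". The component definitions in §8.7.7 compare as follows.

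| Component | What meets the definition | Exposed to the filter? |
|---|---|---|
| Blood loss | Estimated index-procedure loss of at least 1,000 cc | Yes: a volume alone qualifies and need not be a serious event |
| Renal failure | Dialysis, or a >0.5 mg/dL "increase in pre-operative serum creatinine level at two consecutive intervals" | Yes, by the creatinine route: laboratory values alone qualify |
| Myocardial infarction | Raised cardiac biomarkers | Yes: can be non-serious, or labelled unrelated |
| Stroke | Neurological deficit lasting beyond 24 hours | Mainly through the unrelated label |
| Death | Any cause | Least: always serious, and text on all deaths goes to the CEC; read literally, the unrelated label still applies |

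No component carries a relatedness condition, and none requires the serious-event definition to be met.

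**2. Direction.**

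Let Q be the set of patients with at least one qualifying event, and A the set with at least one qualifying event that is also assessed. Every member of A is in Q, so |A| ≤ |Q|. If only CEC-categorized events count, the filtered count cannot exceed the unfiltered one. It is equal when every patient with a filtered MAE has another MAE that is assessed. The comparison is with a CEC assessing all events under the same definitions. It is not with a site-only count, because the CEC may classify as MAE an assessed event that the site did not.

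**3. Size.**

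Input: n = 50, the maximum in §5.1. Each patient whose only MAE is filtered changes the rate by 1/50 = 2.0 percentage points; with fewer patients the step is larger (100/n points).

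The starting counts and losses below are assumptions for illustration. Intervals are exact (Clopper–Pearson) 95%: lower limit = Beta(0.025; x, n − x + 1), upper limit = Beta(0.975; x + 1, n − x), with lower limit 0 at x = 0.

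| Assumed true count | All assessed | One patient lost | Two patients lost |
|---|---|---|---|
| 2/50 | 4% (0.5–13.7) | 2% (0.1–10.6) | 0% (0–7.1) |
| 5/50 | 10% (3.3–21.8) | 8% (2.2–19.2) | 6% (1.3–16.5) |
| 10/50 | 20% (10.0–33.7) | 18% (8.6–31.4) | 16% (7.2–29.1) |

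One lost patient is 1/2 = 50%, 1/5 = 20% or 1/10 = 10% of the count.

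**The case against.** The strongest reply is that the harm is conditional on text not seen. The counting rule may sit in the SAP or the case report forms; for example, blood loss could be counted directly from the recorded volume. Moreover, §10.1 g) describes the CEC's remit without any filter, and §8.7.7 lets the committee obtain operative and progress notes.

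Exposure at 1 month is also small. Death is serious by definition. Paraplegia, prolonged ventilation and stroke will usually qualify as serious, in patients who are still in hospital or just discharged. Few sites would call a stroke soon after aortic repair clearly unrelated. If the undefined creatinine intervals mean scheduled draws, only two fall after the procedure by the 1-month visit (pre-discharge and 1 month). Site data are monitored and queried. Finally, the direction is simple set inclusion, and the illustrated counts are assumed.

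Most of this stands as a limit on size. It does not remove the conflict. The filter is an explicit rule, not a missing detail, and the unfiltered description in §10.1 g) leaves the protocol with two accounts of what the CEC does. If the SAP does have a counting rule, §8.7.7 should cite it, because its sentence as written contradicts §6.1.

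**Conclusion.** The concern holds. Followed as written, the filter in §8.7.7 can drop qualifying events from an endpoint that §6.1 assigns to the CEC, on the strength of labels that the site assigns. The effect on the MAE count is downward or nil.

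This rests on one assumption: that only CEC-categorized events enter the count, as §6.1 and the §8.7.7 Overview indicate, and that the SAP does not say otherwise. The size is 2.0 percentage points per affected patient at n = 50. How many patients would be affected cannot be derived from the documents and is probably few at 1 month. The illustrative intervals overlap and the material reviewed contains no performance goal, so no changed conclusion is claimed. The point should be fixed because it concerns a primary endpoint and the remedy is cheap.

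**What to change.** First check the SAP and the case report forms for a rule on unassessed events. If there is one, cite it in §8.7.7. If not, replace the filter sentence with:

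> All deaths, and every reported event or recorded value that could meet the definition of an MAE component listed in §6.1, are assessed by the CEC regardless of site-reported seriousness or relatedness; other non-serious or clearly unrelated events need not be assessed.

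Support it with two listings: estimated procedural blood loss of at least 1,000 cc (collected under §6.3), and a creatinine rise above 0.5 mg/dL over the pre-operative value at two consecutive intervals (collected under §8.4). Align §10.1 g) with the new wording.

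Separately, §8.7.7 lists Renal Dysfunction (eGFR fall of more than 30%) under Major Adverse Event, while the composite in the synopsis and §6.1 omits it. These passages must be reconciled. The sentence above points to §6.1, so it does not itself bring Renal Dysfunction into the primary endpoint.

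The cost is one sentence in §8.7.7, matching wording in §10.1 g), two listings and a one-line correction. It means a few more CEC cases and possibly a higher reported MAE rate. No new tests or visits are needed.

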8.7.3. Reporting of SAEs

Any SAE occurring during the study period must be recorded on the appropriate **ADVERSE EVENT** CRF and **Serious Adverse Events** section of the CRF.

For any SAE, fax the ADVERSE EVENT CRF within 24 hours of awareness to the Endologix Clinical department at [contact]. All patients with an SAE must be followed and outcomes reported. The Investigator should supply to Endologix and the responsible EC/IRB with a complete, written case history (AE forms) and any additional requested information (e.g., other diagnostic testing, discharge reports, autopsy reports, etc.).

Deaths

For any patient death, regardless of cause or timing, an autopsy should be requested. If the family has agreed to the conduct of an autopsy, the autopsy report is to be attached to the **ADVERSE EVENT** CRF where the death is reported.

A device explant kit will be provided to the hospital for processing and shipment to an independent pathologist per established methods. To request a kit, send a fax to Endologix at [contact], or contact Endologix by telephone at [contact].

In all cases, the death certificate is to be attached to the **ADVERSE EVENT** CRF where the

death is reported. Every attempt should be made to obtain as much detailed information on the events or conditions leading up to the death as possible. If the patient was hospitalized, a copy of the discharge summary source document is required.

Secondary Interventions

For patients that experience any non-diagnostic invasive secondary treatment of the groin access areas or of the abdominal aortoiliac vessels (e.g., hematoma drainage, vascular exploration for bleeding, iliac stenting, thrombectomy, additional device placement for endoleak, embolization for Type II endoleak, etc.), it is important to identify the area, region or vessel segment that is involved and the specific procedure performed on the relevant **ADVERSE EVENT CRF**. A copy of the discharge summary source document is required.

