A letter from the IRB or EC documenting approval of the investigator (must be identified by name), the protocol, (must be identified by title and revision number), and the Patient Information Sheet and Subject Consent Form must be received by ENDOLOGIX or its designee prior to study initiation. A progress report will be submitted by the investigator to the IRB or EC at intervals specified by the IRB or EC, but not less than annually. A copy of this progress report will be sent to ENDOLOGIX. After completion of the study, the investigator will submit a signed clinical safety summary of the study to the IRB or Written responses from the relevant Competent Authority and any other local approvals must also be obtained prior to starting the study.

- d) *Ethical Conduct of Study*: The study will be conducted in accordance with GCP as contained in the ICH Guidelines and US CFR governing the protection of human subjects (Title 21, Part 50) and the obligations of clinical investigators (Title 21, Parts 312.60 through 312.69). ENDOLOGIX is responsible for the ongoing safety of the device and will promptly notify all participating investigators and regulatory authorities of findings that could adversely affect the safety of subjects, affect the conduct of the study, or alter the IRB/EC's approval to continue the study.
- e) *Core Lab*: The Core Lab is responsible for the three-dimensional reconstructions and assessment of all submitted CT scans preoperatively and imaging postoperatively and for reporting of results.
- f) *Data Management Group*: The data management group is responsible for database development, validation, control and management of input from monitored CRFs, issuance and resolution of queries, database maintenance, and reporting for statistical analysis.
- g) *Clinical Events Committee*: The independent clinical events committee will consist of at least three physician members and is responsible for review of events and complications documented on CRFs and in source documents by the study investigators during the trial, and for categorization of these events according to the event definitions and primary endpoint criteria in this protocol. Reviews will occur on an ongoing basis throughout the trial as events are reported. The adjudicated events will be reviewed by the Data Safety Monitoring Board.

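### The last limb of the aneurysm-related death definition has no time window or causal test, so applied as written it counts unrelated late deaths after re-treatment

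*Combined protocol and SAP*

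**What the plan says.** Section 8.7.7 of the protocol divides deaths into early and late at 30 days. It then adds a second split: "It will also be subcategorized as aneurysm-related or not aneurysm-related". Aneurysm-related death has three limbs:

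1. death from any cause within 30 days of the procedure;
2. death caused by rupture of the aneurysm;
3. death after a procedure aimed at the aneurysm.

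Limbs 2 and 3 share one phrase: "death due to aneurysm rupture or following any procedure intended to treat the aneurysm".

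The CEC applies the definition. Section 10.1(g) gives it "categorization of these events according to the event definitions and primary endpoint criteria in this protocol", and section 8.7.7 states: "Analyses of events described in this protocol will be based on the CEC-determined categorization". On what the CEC sees, section 8.7.7 says two things. The sponsor sends it "the complete case report form event text that details all deaths", but "Non-serious events or events that are reported as clearly unrelated events will not be assessed by the CEC".

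Section 6.3 lists all-cause and aneurysm-related mortality within 30 days, at six months and yearly from year 1 to year 5. Its footnote refers to section 8.7.7 for event definitions, so the definition governs this evaluation as well as the primary endpoint.

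**The concern.** Limb 1 is bounded by time and limb 2 by cause. Limb 3 rests on the word *following* alone, with no number of days and no requirement that the procedure contributed to the death. Follow-up runs to five years, and section 5.3 excludes only patients with a life expectancy under two years, so unrelated late deaths are foreseeable. Where the patient has had an intervening re-intervention or conversion, the text as written makes such a death aneurysm-related.

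At stake is whether late aneurysm-related mortality rests on a rule that two assessors would apply in the same way. The study is meant to support regulatory submissions, and this limb can only push the figure upwards.

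**Working it through.** The documents give no rate or target for this evaluation, so there is no plan figure to reproduce. The check is of the text, followed by simple arithmetic for scale.

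**Step 1: does other text supply the missing bound?**

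- The early/late split in 8.7.7 is a separate subcategory and sets no window for limb 3.
- Conversion to open repair, as defined in 8.7.7, may happen at any point after initial success and for any reason. Secondary procedure has no time limit either.
- The event definitions in 8.7.7 open with a general sentence asking that events be linked, where possible, to the aneurysm procedure or to closure of the access site. It is not a condition of aneurysm-related death.
- Section 8.7 says that "relationship to the device, and relationship to the procedure will be identified by the Investigator". It does not ask for relationship to the aneurysm.

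None of these supplies a window or a causal test for limb 3.

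**Step 2: apply the definition to hypothetical deaths.** Reading A takes limb 3 to mean procedures after the index repair. Reading B also counts the index repair.

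| Death | Reading A | Reading B |
|---|---|---|
| Day 20, any cause | related (limb 1) | related |
| Year 3, rupture | related (limb 2) | related |
| Year 3, unrelated, no later procedure | not related | related (limb 3) |
| Year 3, unrelated, endoleak re-intervention at year 1 | related (limb 3) | related (limb 3) |

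Reading A is the more sensible: limb 1 refers to a single procedure and limb 3 to any, and the protocol requires a class of deaths that are not aneurysm-related. Reading B would leave that class empty after implant and make limb 1 redundant. The last row is misclassified under both readings.

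**Step 3: the CEC filter.** If the site reports the last-row death as clearly unrelated, the CEC may not assess it, and it then has no CEC category. If the site does not, limb 3 applies. Similar deaths can therefore end up differently according to the site's label.

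**Step 4: size.** The shift in the crude rate per affected death is 1/n.

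- n = 50 (maximum, section 5.1): 1/50 = 2.0 percentage points.
- n = 40 (assumed, for scale): 1/40 = 2.5 points.
- n = 30 (assumed, for scale): 1/30 = 3.3 points.

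Exact (Clopper-Pearson) 95% intervals at n = 50, with the number of deaths assumed:

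| Deaths counted | Rate | 95% interval |
|---|---|---|
| 0 | 0% | 0 to 7.11% |
| 1 | 2.0% | 0.05 to 10.65% |
| 2 | 4.0% | 0.49 to 13.71% |
| 3 | 6.0% | 1.25 to 16.55% |

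An affected death needs three things: a later aneurysm procedure, an unrelated death after day 30, and CEC assessment of that death. The documents give no rate for any of them. For deaths up to day 30 the shift is 0, because limb 1 already counts them all.

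**The case against.** The strongest reply is that nobody would apply limb 3 mechanically. The CEC consists of independent physicians who may request operative notes and autopsy reports, the term being defined is aneurysm-*related* death, and the general sentence in 8.7.7 points them towards relatedness. The filter for clearly unrelated events may also remove the very deaths in question. Much of this stands: a CEC would probably read in some limit. But the limit would be the CEC's own, while 8.7.7 promises standardized definitions. The filter does not settle the matter either, because the same section sends the CEC the text on all deaths and requires each death to be subcategorized.

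A second reply is that inclusive counting is a defensible, conservative choice in a single-arm safety study, since limb 1 already ignores cause and the error runs against the device. That holds for a bounded window. It does not explain an open-ended one lasting five years.

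A reader might go further and infer that the safety conclusion is compromised, or that late aneurysm-related mortality will certainly be overstated. The documents support neither. The primary safety endpoint is assessed at 1 month and counts death from any cause. The supplied text attaches no hypothesis or threshold to aneurysm-related mortality, and the number of affected deaths may be nil. Doubtful cases can also be traced: "In all cases, the death certificate is to be attached" to the adverse event form.

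**Conclusion.** The gap is real and minor. As written, limb 3 classes unrelated late deaths after re-treatment as aneurysm-related. If the index repair is counted as well, it conflicts with limb 1 and with the class of deaths that are not aneurysm-related. The effect is confined to late aneurysm-related mortality: 2.0 percentage points per such death in the crude rate if all 50 patients are in the denominator, and more with fewer. All-cause mortality, the primary endpoint and deaths to day 30 are unaffected.

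This rests on the CEC applying the definition as worded, and on nothing in Attachment 5 overriding it. That attachment is the statistical analysis plan; it is listed but its text was not supplied, so a clarifying rule there cannot be ruled out.

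**What to change.** - **Definition.** Keep the first two limbs and bound the third, for example: *or death within 30 days of, or adjudicated by the CEC as caused by, a secondary procedure or conversion to open repair performed after the index procedure*. The 30 days reuse the window of limb 1; the length is the sponsor's choice. Add no new cause categories. Extending the definition to late deaths caused by the device or the index repair would widen the evaluation, and this gap does not require it.
- **CEC process.** State that the CEC assigns the aneurysm-related or not aneurysm-related subcategory to every death, so that the filter for clearly unrelated events leaves none unclassified.
- **Consistency and timing.** Check the wording against Attachment 5 and apply it prospectively. If late deaths have already been classified, report them under both the existing and the revised definition, because the change would be made with outcomes known.

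The cost is one sentence in the definition, one in the CEC process text and the check against Attachment 5. No new site data are needed: the CEC already receives the event text on all deaths, and death certificates are already required. The downside is slightly more CEC work and possibly one extra table.
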